**(2) Neurophysiologic Assessment:** The following neurophysiologic assessments will be performed at the Department of Anesthesiology Clinical Research Section (Room 1487 Jelke), where the PI or Co-PI ([name]) will supervise the RN in the performance of these tests. These assessments have been performed by the PI and [name] (Co-investigator) for other clinical and basic research respectively.

**(a) Thermal pain stimulation:** Prior to surgery, a heat probe (3x3 cm; TSAll instrument; Medoc®) will be applied 16 cm above the center of the patella as a measure for **thermal pain sensitivity**. Probe temperature will be ramped up from 32° C at a rate of 4°C/sec until 47 °C is reached, and then maintained for 5 sec. After the 5 sec period, subjects will rate pain intensity (0-10 NRS scale). If subject requests removal of probe before 5 sec period due to intolerable discomfort, it will be removed and a maximal value of 10 will be given. The test will be repeated 4 times and the average of the responses will be calculated. This procedure will be repeated on the contralateral leg. **(b) Examination of the knee for peripheral neuropathic pain (StEP)** using the following 9 parameters and calculating a score to determine the presence of neuropathic pain (total score ≥ 4). The StEP will detail the symptoms and signs of the pain in the knee. This test will be performed 5 cm medial and 5 cm rostral to the center of the patella on the un-operated knee as a control and then the operated knee.

- Sympathetic: Recording of skin characteristics (yes/no evaluation of color, sweating, trophic changes)
- Tactile allodynia (touch): Numbness, allodynia or hyperalgesia to von Frey filament stimulation, with corresponding NRS pain intensity
- Tactile hyperalgesia (blunt pressure): Decreased or increased response, with corresponding NRS pain intensity
- Dynamic tactile allodynia (brush movement): Decreased or increased response, with corresponding NRS pain intensity
- Vibration sense (tuning fork): yes/no to decreased response to stimulation at the tibia bone ventral midline, 15 cm below lower point of proposed incision
- Evoked pain (pinprick): decreased or increased response, with corresponding NRS pain intensity
- Non-painful warm stimulus (TSAll instrument, Medoc®): decreased or increased response, with corresponding NRS pain intensity

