#### **Long-term Assessments (same methods used pre-surgery):**

(1) **Pain Intensity:** NRS of the operated knee will be obtained by RN from the patients at the 3 wk, 6 wk, 3 mo and 6 mo scheduled visits.

(2) **Neurophysiologic Assessment** will be performed at the 6 mo scheduled visit.

(a) *Examination of the knee for peripheral neuropathic pain (StEP)*

(3) **Psychosocial Measures:** Beck Depression Inventory will be administered at 6 mo by RN.

(4) **Functional Measures:** ROM, WOMAC and SF-36 questionnaires will be administered at 3 wk, 6 wk, 3 mo and 6 mo.

(5) **Skin Temperature:** Skin temperature will be performed at 6 months

**Patients who have NRS $\geq$ 4 at three wks and beyond:** For patients having NRS $\geq$ 4 at 3 wk and beyond, the oral opioid regime will be continued. If the hydrocodone/acetaminophen regime does not maintain a NRS $<$ 4, then oral long-acting opioids such as time-release oxycodone 10 mg twice/day will be prescribed. The purpose of closely following the analgesics and NRS for the study patients is to ensure that at the 6-mo time point the analgesic consumption is within a standard protocol for all patients, whether they do or do not have PPP. Patients who have persistent pain at the 3 and 6-mo visits will be evaluated by the orthopedic surgeon for prosthetic-related failure. An examination will be performed to evaluate instability of the tibial femoral joint or patellar maltracking. Plain radiographs will be reviewed by the orthopedic surgeons (Co-investigators) for evidence of prosthetic loosening, malposition and patellar maltracking, as well as overall axial alignment to ensure coronal alignment is within the range of neutral to 10 deg of valgus. If this evaluation is negative, an erythrocyte sedimentation rate (ESR) and C-reactive protein (CRP) measurement will be obtained as a screening tool for infection. If these indices are abnormal (ESR $>$ 30 mm/h; CRP $>$ 10 $\mu$ g/mL), an aspiration of the knee will be performed, including a synovial fluid white blood cell count with differential and culture to rule

out infection. These parameters are based on previous work by [name] (Co-investigator) in this specific topic.

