model fit will be evaluated for all models. **Moderating** effects will be tested using model building with predefined interactions for linear or logistic models.

Due to the extensive monitoring designed into our protocol we do not expect a large amount of missing data; however, the missing data that does arise will be handled using multivariate multiple imputation. Data not assumed to be missing at random, will be evaluated for systematic effects using sub-groups stratification. Statistical analyses will be performed using SAS version 9.1 (SAS Institute Inc, Cary, NC) or SPSS (SPSS for Windows, Rel. 16.0.1. 2007. Chicago: SPSS Inc.), with statistical significance determined with a Type I error threshold of  $\alpha = 0.05$ . For continuous outcome mediation analysis we will use a SAS macro (INDIRECT macro) and for dichotomous outcomes the SPSS macro version (INDIRECT macro) will be used, as the SAS macro version does not allow for dichotomous outcome variables.

**Primary endpoint:** The *primary endpoint* for the **Primary Aim** will be the incidence of PPP after TKR (similar to our power analysis), evaluated at 6 mo. For the **Secondary Aims**, the *primary endpoint* will be functional outcomes (ROM, WOMAC, SF-36,).

**Secondary endpoints:** The *secondary endpoint* for the Primary and Secondary Aims will examine additional parameterizations of PPP at 6 mo (NRS pain non-dichotomous, StEP neuropathic pain examination). Use of raw NRS pain scores may highlight functional (e.g. linear) relationships between pain and the predictive factors. Analysis will be performed as described for the primary outcome variable (incidence of PPP) but with the re-parameterized outcome variable and different model assumptions, depending on distributional properties. Each re-parameterization will be evaluated with respect to and compared with the primary outcome.

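### The 6-month StEP neuropathic-pain endpoint has no knee-pain condition, no stated item scoring and no adjustment for the preoperative score, although it stands in for PPP

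*Combined protocol and SAP*

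**What the plan says.** The protocol and SAP are one document.

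- **The instrument.** Under Approach, Neurophysiologic Assessment (b), the knee is examined "using the following 9 parameters" and the result is used by "calculating a score to determine the presence of neuropathic pain (total score ≥ 4". The un-operated knee is tested first, as a control.
- **The items.** The touch item covers "Numbness, allodynia or hyperalgesia to von Frey filament stimulation", with an NRS rating. The pressure item reads "Tactile hyperalgesia (blunt pressure): Decreased or increased response, with corresponding NRS pain intensity". Brush, pinprick, warm and cold have the same two-directional form. Vibration is a yes/no for a decrease. The sympathetic item is "Recording of skin characteristics (yes/no evaluation of color, sweating, trophic changes". Temporal summation is a yes/no for increased pain.
- **When and in whom.** StEP is done before surgery. Under Long-term Assessments the neurophysiologic assessment "will be performed at the 6 mo scheduled visit", with no restriction to patients in pain.
- **Its role.** The Secondary endpoints paragraph lists "additional parameterizations of PPP at 6 mo (NRS pain non-dichotomous, StEP neuropathic pain examination" and says each of these will be compared with the primary outcome.
- **The construct it re-expresses.** Under Overall Strategy, PPP is pain in the operated knee at six months with NRS ≥4 and other causes excluded.
- **Covariates.** The Covariates paragraph names age, weight/BMI, OA severity, ASA status, analgesic consumption, duration of surgery, complications and early postoperative opioid use. The preoperative StEP result is not among them.

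**The concern.** An alternative version of PPP should keep what defines PPP, namely pain in the operated knee. The non-dichotomous NRS does. The StEP result, as written, need not: it is a sensory examination given a pain label by a cut-off, and nothing ties that label to a pain report.

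This matters here because the test site lies near a surgical wound and the plan itself looks for sensory loss. Overall Strategy names postoperative numbness as a possible risk factor, the acute assessments map areas of numbness, and the limitations section says minor nerve damage cannot be assessed directly. If decreased sensation scores, part of the outcome could be loss of feeling around the incision. Associations with the risk factors, and the comparison with PPP, would then be read as findings about neuropathic pain. If an area of numbness were also used as a predictor, the same phenomenon would sit on both sides of the model.

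Separately, the aim concerns the development of PPP. Without the preoperative StEP result in the model, signs present before surgery are treated like new ones.

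**Working it through.** **1. The plan's own figures.** The text announces nine items, and nine are listed, so the count agrees. The cut-off of 4 cannot be reproduced, because no points, direction or weights are given for any item.

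**2. Direction recorded by each item** (Neurophysiologic Assessment (b)).

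| Item | Records a decrease | Records an increase or pain |
|---|---|---|
| Sympathetic signs | no | no |
| Touch | yes | yes |
| Blunt pressure | yes | yes |
| Brush | yes | yes |
| Vibration | yes | no |
| Pinprick | yes | yes |
| Warm | yes | yes |
| Cold | yes | yes |
| Temporal summation | no | yes |

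Items recording a decrease: 7 of 9. Vibration is tested on the tibia, 15 cm below the lower end of the planned incision. At the site beside the patella the count is therefore 7 − 1 = 6.

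**3. Highest score from decreased sensation alone.** The scoring is not stated, so two rules are assumed.

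- Rule A, one point for any abnormal item: at most 7, or 6 without vibration. Both exceed 4, so a pain-free patient with numb skin can be a case.
- Rule B, one point only for an increased or painful response, except that reduced vibration sense scores: at most 1, or 0 without vibration. Both are below 4, so such a patient cannot be a case.

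The documents do not decide between A and B.

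**4. Does Rule B remove the problem?** Only for numbness. Seven items record an increased or evoked response (touch, pressure, brush, pinprick, warm, cold, temporal summation). A patient whose knee NRS is 0, but who reacts abnormally on four of them, still scores 4 under Rule B. The missing pain condition therefore matters under either rule.

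**5. Pain condition.** Setting the StEP text, the 6-month visit, Long-term Assessments and Secondary endpoints side by side, none makes knee pain a requirement for a StEP case.

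**6. Baseline.** StEP is performed before surgery and repeated at 6 months by the same method. The Covariates paragraph does not include the preoperative result, and no change-from-baseline definition is given.

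**7. Case numbers.** The planned completers are 300 × 0.85 = 255. At the 17.8% incidence used for the sample size, 255 × 0.178 ≈ 45 would have PPP and 255 − 45 = 210 would not. To go further one needs the frequency of StEP ≥4 among patients with NRS 0. The documents give neither that, nor a frequency of numbness, nor the share of the 210 with NRS 0. The calculation stops here.

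**The case against.** The strongest reply is that the item list says what is recorded, not what scores. The scoring belongs to the cited instrument, and it may give decreased responses no weight. That stands: nothing in the documents shows that numbness reaches the cut-off. A reader might infer that a pain-free patient with numb skin does count as a case. The text supports only that such a patient could, depending on scoring.

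A reader might also take the roughly 210 patients without PPP, assume a rate of numbness, and quote a number of false cases. The documents do not support this. They give no such rate. The 210 are patients with NRS below 4, not pain-free patients, and the preliminary NRS scores had modes at 0 and 3, so many of them may have some knee pain. The references to numbness concern the acute period or name it as a risk factor. They do not show that it persists to 6 months or reaches the StEP site. The Primary Aims list under Detailed Analyses also omits numbness, so the overlap of predictor and outcome is a possibility, not a stated model.

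Three further replies carry less weight. The un-operated knee serves as a control, but how it enters the score is not stated, and one-sided loss from an incision would show up in a side-to-side comparison. The plan describes StEP as detailing signs and symptoms of knee pain, but that is a description, not a case rule. The promised comparison with the primary outcome could expose StEP cases without PPP, but it would not redefine them. It is also fair that Secondary endpoints does not repeat the ≥4 cut-off, so the endpoint might be the score itself. That adds to what must be specified, and a score can be raised without pain just as a dichotomy can.

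**Conclusion.** The point holds as a defect of definition in one secondary endpoint. Three facts rest on the text alone: StEP serves as a version of PPP without a knee-pain condition; item points, direction, use of the control knee, and the choice between score and cut-off are unstated; and the preoperative result is collected but not listed as a covariate.

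Whether numbness alone can make a case depends on the scoring: a maximum of 6 or 7 under one assumed rule, 0 or 1 under the other, against a cut-off of 4. The effect on the number of cases, and on any estimated association, cannot be computed from the documents. The primary endpoint, its analysis and the sample size are not touched. The change is worth making before the data are analysed, because the label neuropathic pain would otherwise go further than the definition.

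**What to change.** - Define a 6-month neuropathic-pain case as StEP ≥4 in the operated knee together with operated-knee NRS ≥1, and give a sensitivity version with NRS ≥4. Making NRS ≥4 the main condition is less attractive: with other causes excluded, the endpoint becomes a subset of PPP and drops neuropathic pain at NRS 1–3. Use the same NRS (rest or movement) that defines PPP, and say which it is.
- Keep all examined patients in the denominator. Report StEP ≥4 with NRS 0 separately, as sensory abnormality without pain.
- Adjust the StEP model for the preoperative StEP score, kept in the model whatever the backward selection does.
- State the points and direction for each item, how the NRS ratings and the un-operated knee enter, and whether the endpoint is the score or the cut-off.

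The cost is SAP wording. NRS and preoperative StEP are already collected, so no visit or measurement is added. The price is fewer cases, and so wider intervals, for this secondary endpoint.

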(b) *Western Ontario and McMaster Universities Osteoarthritis Index (WOMAC):* A widely used measure of symptoms and physical disability specifically designed for patients with OA of the lower extremity. This instrument evaluates 3 dimensions: pain, stiffness and physical functional disability (permission obtained).

(c) *SF-36 (SF-36):* A self-report survey containing 36 items and is the most commonly used measure of physical functioning. The SF-36 is a general measure of health status as opposed to one that targets specific population. Accordingly, the SF-36 can provide a benchmark with which to compare specific populations. It has well described properties and sensitivity (permission obtained for current study use).

**(5) Skin Temperature:** Skin temperature, the abnormalities of which have been associated with neuropathic pain conditions, will be measured medial and lateral to the center of the patella on the operated knee, and on the contralateral knee, as is standard at the Rush Pain Center.

**Day of surgery:** Patients will not receive oral adjuvant analgesics preoperatively on the day of surgery. The method of anesthesia for the case will be that which is deemed appropriate by the attending anesthesiologist. For patients receiving general anesthesia, standard anesthesiology practice will be followed. In the case of patients receiving epidural anesthesia, on the morning of surgery, patients will be sedated with midazolam (0.05 mg/kg titrated to effect) and an epidural catheter at the L3-L4 or L4-L5 vertebral level. This procedure will be carried out in the designated regional room with the patient in sitting position. The skin will be infiltrated with lidocaine and using an 18G Touhy needle®, the epidural space will be identified via the loss of resistance technique with air and glass syringe. A 20G catheter will then be threaded 3-5 cm in the epidural space and a test dose with 1.5% lidocaine and epinephrine will be performed. The PI will place all the epidural catheters for consented study patients, to minimize variability.

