**Post-Incision to Hospital Stay:** *Acute postoperative pain management:* For patient's that received general anesthesia, standard post-operative analgesic practice will be followed. For patients with epidural catheters in place, an epidural infusion of bupivacaine (0.1%) and fentanyl (5 µg/ml) will be started upon entry to the recovery room, using a continuous basal infusion at 6 mL/h with superimposed patient-controlled epidural analgesia (PCEA) bolus dose of 1 mL every 15 min, with a 4 h lockout of 40 mL to be delivered by the infusion pump. Patients will be instructed prior to surgery, on PCEA operation (routine clinical practice) by the acute-pain service nurses, who report to the PI. If the patient complains of severe pain, the acute pain nurse will be

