contacted and the epidural infusion titrated (per previous published protocol). However, if these measures fail and the patient has severe pain, intravenous opioids (morphine 2 mg bolus) will be administered. Records will be kept of the total amount of epidural solution consumed, including morphine boluses, in increments of 4h for the 24h postoperative period. After 24 hours, the epidural catheter will be removed. We customarily administer warfarin (oral 5 mg) for deep venous thrombosis prophylaxis on the night of TKR. An International Normalized Ratio will be obtained prior to removing the catheter. Once the epidural catheter is removed, all patients will receive hydrocodone 10 mg/acetaminophen 325 mg, 1-2 tablets every 4-6h depending on the NRS pain score for a maximum of 6 tablets/ day (to keep within current geriatric guidelines <3.25 mg/day acetaminophen), until discharged from the hospital. Patients having NRS  $\geq 4$  for more than 1h will receive intravenous morphine 2-4 mg as needed every 15 min for a maximum of 15 mg over a period of 2h. Patients allergic to intravenous morphine or oral hydrocodone will receive an equivalent dose of intravenous hydromorphone or oral oxycodone respectively. All analgesics administered over 0-72h will be recorded in the data collection book for inclusion as covariates in analyses. Although a more complex algorithm for pain management, including multimodal non-opioid analgesia, could be used and continued for at least 2 wks later, those analgesics might become factors themselves that influence the development of PPP, and therefore will not be used in this proposed study. We will also obtain a 5mL blood sample for RNA analysis during the hospital stay (when wound inflammation is maximum).

[figure not shown]
**Postoperative Management:** Routine vital signs will be recorded on the floor and transferred to the data collection book. The patients will undergo routine physical therapy sessions twice/daily until they meet the hospital discharge criteria as determined by the therapist.

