#### Acute Postoperative Assessments (total time approximately 30 min):

**(1) Pain Intensity:** The 11-point NRS pain intensity will be recorded every 4h for 0-72h postoperatively of the operated knee, then twice daily thereafter until discharge. The area-under-curve (AUC) for NRS over 0-72h will be calculated and interpreted as the burden of acute postoperative pain.

**(2) Neurophysiologic Assessment of mechanical (punctate) hyperalgesia and hypoalgesia** will be performed at least 6 hours after removal of epidural, post-incision by the RN under the supervision of PI. The elasticized (ACE) wrap around the knee will have already been removed at 24h post-incision. With the subject in a relaxed supine position with eyes closed, stimulation with a hand-held von Frey filament (4 g) will begin on the lateral aspect of the knee where the patient reports no pain sensation (Figure below), and move in 2 cm steps toward the incision until the subject reports a distinct change in sensation. The first point where the subject reports the sensation as 'painful', 'sore', or 'sharper', will be marked with an alcohol pen. To map the area of this mechanical sensitivity around the knee, testing will be done every 2.5 cm around the mid-line along radial lines. If no change in sensation is found, stimulation will be stopped at 5 cm from the surgical incision to restrict our testing to the area of **secondary mechanical hyperalgesia**. Any areas of numbness will also be noted. To quantify the area, a transparent plastic sheet with pre-marked grid marks will be placed over the knee to facilitate the transfer of the skin markings to our template. The area will then be measured with a digital planimetry software.

(a): In preliminary studies we found the mean area to be 37 cm^2. Areas of numbness will also be noted.

**(3) Functional Measures (ROM only):** The active and passive ROM of the knee will be recorded every day in the hospital by the physical therapist. In addition, the RN will measure active and passive ROM at least 6 hours

after removal of epidural, (performed at the same time as assessment of mechanical (punctate) hyperalgesia and hypoalgesia.

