**Covariates:** Preoperative covariates included are as follows: age, weight/BMI, OA severity and ASA status. Perioperative covariates include: postoperative analgesic consumption and duration of surgery. Complications after TKR will be recorded and included as a summed incidence. Patient questionnaires of drug use in the first three wks postoperatively will be converted to daily morphine equivalents and included as a covariate in the predictive models. Although the protocol stipulates uniformity in medication use during the acute postoperative period, once the patient leaves the hospital, their analgesic use over the next 6 mo cannot be rigidly controlled. To reduce variation we will prescribe analgesics as needed (per protocol above mentioned) and will remain in contact with the patients to record additional medication.

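### Anesthetic technique is not a named covariate although analgesia in about the first 24 h differs by technique, so acute pain and hyperalgesia area may partly reflect it

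*Combined protocol and SAP*

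**What the plan says.** *Choice of technique.* Under Day of surgery: "The method of anesthesia for the case will be that which is deemed appropriate by the attending anesthesiologist". For one group the intraoperative regimen is left open: "For patients receiving general anesthesia, standard anesthesiology practice will be followed".

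*Acute analgesia.* Under Post-Incision to Hospital Stay the two groups separate again. For one, "For patient's that received general anesthesia, standard post-operative analgesic practice will be followed". For the other, "For patients with epidural catheters in place, an epidural infusion of bupivacaine (0.1%) and fentanyl (5 µg/ml) will be started upon entry to the recovery" area, with a stated basal rate and patient-controlled boluses; the catheter comes out after 24 h, once an INR has been obtained. One oral opioid regimen then applies to all patients, but its start is defined by catheter removal. The same section excludes multimodal non-opioid drugs from the study because "those analgesics might become factors themselves that influence the development of PPP". It also says that all analgesics given over 0-72 h are recorded for use as covariates.

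*The two exposed measurements.* Under Acute Postoperative Assessments, "The area-under-curve (AUC) for NRS over 0-72h will be calculated and interpreted as the burden of acute postoperative pain", and the punctate hyperalgesia mapping "will be performed at least 6 hours after removal of epidural, post-incision by the RN". The study calendar marks neurophysiologic assessment at 36 h post-incision. Detailed Analyses lists postoperative pain intensity and hyperalgesia area as primary-aim risk factors, and makes area the mediator in Hypothesis 2.

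*Covariates.* The paragraph contrasts the acute phase with the period after discharge: "Although the protocol stipulates uniformity in medication use during the acute postoperative period". It names age, weight/BMI, OA severity, ASA status, postoperative analgesic consumption, duration of surgery, complications, and three-week drug use in morphine equivalents. Technique and the hour of mapping are not named.

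**The concern.** Technique is neither fixed nor randomised, and the documents do not say on what grounds it is chosen. It may shift both the early NRS scores and the mapped area. If it is also related to PPP, it confounds the association of either measure with PPP. In Hypothesis 2 it would be a common cause of mediator and outcome, which biases the indirect effect that the hypothesis is about. If it is unrelated to PPP and moves only the measurement, it adds variance that weakens true associations.

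The plan accepts the principle itself: it bars some analgesics because they could influence PPP, and one operator places every epidural catheter to limit variability. The difference between a neuraxial infusion and none is then left without a model term of its own.

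**Working it through.** The plan gives no figure on this point, so there is none to reproduce. The check compares the passages and then sizes the effect under stated assumptions.

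**1. Uniformity.** Covariates says acute medication use is uniform by protocol. Post-Incision to Hospital Stay gives one group a specified infusion and the other an unspecified practice. For about the first 24 h these cannot both hold. That period is 24/72 = one third of the AUC window.

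**2. Mapping time.** Removal at 24 h plus the 6 h minimum gives 30 h, which is compatible with the calendar's 36 h. The two rules conflict if the catheter comes out later than 36 - 6 = 30 h post-incision. For a patient without a catheter, only the calendar's nominal time applies. The text sets no upper limit for anyone.

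**3. Dilution if technique moves only the measurement.** Let p be the share in one technique group and d the shift in within-group SDs. Technique adds variance p(1-p)d², so a linear slope (taken as an approximation to the logistic one) is diluted by p(1-p)d² / [1 + p(1-p)d²]. Both p and d are assumptions.

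| p | d | p(1-p)d² | dilution |
|---|---|---|---|
| 0.1 | 0.5 | 0.0225 | 2.2% |
| 0.1 | 1.0 | 0.09 | 8.3% |
| 0.3 | 0.5 | 0.0525 | 5.0% |
| 0.5 | 0.8 | 0.16 | 13.8% |
| 0.5 | 1.0 | 0.25 | 20.0% |

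On the NRS scale, take the plan's SD of 2.9 and an assumed shift of 0.5-2 points with a share of 10-50%. The part of the variance due to technique runs from 0.09 × 0.25 / 8.41 = 0.3% to 0.25 × 4 / 8.41 = 12%.

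**4. Confounding if technique also affects PPP.** All inputs here are assumed.
- Area, 50/50 mix, shift 0.5-0.8 SD, technique-PPP odds ratio 1.5-2.0, no true area effect: simulation gives a spurious odds ratio of about 1.04-1.13 per SD. With technique in the model it returns to 0.99-1.00.
- Acute NRS, n = 255, general-anesthesia share 25-50%, shift 1-2 points, the same technique odds ratios, no true NRS effect: the spurious odds ratio is 1.01-1.04 per point and rejection is 5-10%, against about 4-6% with technique included.
- If technique shifts only the measured NRS, a true odds ratio of 1.24 (the plan's preliminary estimate) appears as about 1.21-1.24.

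**5. Precision available.** From the sample-size paragraph, 300 × 0.85 = 255 completers, and 255 × 0.178 = 45 expected PPP cases. The unadjusted standard error of a log odds ratio per SD is about 1/√(255 × 0.178 × 0.822) = 0.16. The spurious log odds ratios for area in step 4 are ln 1.04 = 0.04 to ln 1.13 = 0.12, all below one standard error.

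**The case against.** Much of the exposure is already limited.

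- *Analgesic covariates.* A reader might infer that acute analgesia goes unadjusted because epidural bupivacaine has no morphine equivalent. The documents do not support that. Morphine equivalents are specified only for the three-week questionnaires. The 0-72 h drugs are a separate covariate, and epidural volume is logged every 4 h. Entered as its own term, that volume would be zero under general anesthesia and about 6 mL/h × 24 h = 144 mL from the basal rate alone in epidural patients, so it would nearly encode technique. This stands. What remains is that the plan does not say how these drugs are coded, and that consumption itself responds to pain.
- *Uncontrolled analgesia.* A reader might infer that general-anesthesia patients are uncontrolled throughout. The multimodal exclusion is worded for the whole study, the later oral regimen is for all patients, and inclusion requires consent to the standard anesthetic and analgesic protocol. The charge is firm only for about the first 24 h. It is unclear whether the later rules override the open wording for general-anesthesia patients.
- *Mapping time.* It is not wholly undefined. The calendar gives 36 h, and Standard TKR makes incision time zero.
- *Real exposure.* If an epidural lowers pain, a lower AUC is a true lower burden and not measurement noise. Hypothesis 1 serves clinical prediction, where a predictor correlated with technique is not in itself a defect. This stands, and puts the weight on Hypothesis 2.

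**Conclusion.** The point holds as a contradiction on acute uniformity, a missing named covariate, and a mapping rule that does not fit every patient. Acute NRS and hyperalgesia area may partly reflect technique, with the main consequence in the Hypothesis 2 mediation models.

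The size is unknown. Under the assumed ranges it is small to moderate: roughly 2-20% dilution, or a spurious odds ratio up to about 1.13 per SD if technique also affects PPP. It would be slight if nearly all patients receive one technique; the documents detail only the epidural pathway, so general anesthesia may be a minority.

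A reader might infer that the primary results would be invalid or substantially biased. The documents do not support that: they give no technique share and no technique effect, and the biases computed for area are below one standard error at the planned size. The case for acting is that a possible confounder, already known for every patient, can be removed cheaply.

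**What to change.** - **Covariates.** Add technique (epidural versus general) as a prespecified covariate in both the mediator and outcome equations of Hypothesis 2. For Hypothesis 1, include it at least in a prespecified adjusted analysis. State how a patient who has both is coded, and how epidural and systemic drugs enter the 0-72 h analgesic covariate.
- **Acute Postoperative Assessments, mapping.** State the time from incision for all patients, consistent with the calendar's 36 h and keeping the existing minimum interval after catheter removal. Record the actual hour for use as a covariate.
- **Acute pain.** Keep the 0-72 h AUC and add a sensitivity AUC restricted to the period after actual catheter removal in epidural patients, with the corresponding hours in general-anesthesia patients. A fixed 24-72 h window would not do: removal follows 24 h and an INR, so an infusion may still be running.
- **Text.** Correct the uniformity statement. Reconcile the passages on acute analgesia, so that it is clear whether the all-patient oral regimen and the multimodal exclusion apply to general-anesthesia patients. No clinical rule is proposed here.

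The cost is wording, one recorded time, and one or two extra terms. With about 45 expected events and a covariate list that is already long, those terms are not free. That is why an adjusted analysis, rather than a mandatory term in every model, is enough for Hypothesis 1.
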